5.5 Data Collection

Patients will be followed over time and all surveys will be administered as described in Table 1 (Section [7](#)).

Rev. 11/16

- 5.5.1 Following site randomization and local IRB approval, a consent form will be given to each provider (oncology staff, i.e. MD, nurse practitioner or PA-C, that clinically assesses the patient). A signed provider consent form is required for participation.
- 5.5.2 Upon site study activation a delegation of responsibility log should be completed and submitted to CTSU prior to enrolling the first patient
- 5.5.3 Patients will be recruited to participate at their scheduled provider appointment. Study staff will approach patients who are possible candidates to determine interest. If interested, eligibility will be confirmed (Section [3](#)).

Rev. 11/17

- 5.5.4 A consent form will be given to interested and eligible patients. The consent form should be completed on the same day eligibility is confirmed, however, it must be signed prior to treatment initiation (See Section [7](#) Patient-specific timeline).
- 5.5.5 Patient will have the baseline provider visit, complete baseline surveys and be registered to the trial on the same day of consent. If this is not feasible, then all baseline requirements (including registration) must be completed within one week of patient consent. Baseline provider visits, completion of baseline surveys and study registration must be completed on same day. (Table 1).
- 5.5.6 The designated research staff person (CRN or CRA) from each institution will administer questionnaires and assist with the completion of form(s) at the baseline and follow-up visits, as necessary. A CRN or CRA must review form(s) for completeness as

soon as the patient finishes them to ensure all items have been marked appropriately.

- 5.5.7 The scheduled study tools must be completed during the visit.
- 5.5.8 Completed clinician and patient form(s) will be entered into Medidata Rave within 7 days of collection.

5.6 Administration Instructions

- 5.6.1 The forms must be administered at the time points noted in Table 1 (Section [7](#)).
- 5.6.2 The CRA should read the instructions at the beginning of each questionnaire and administer to the patient unless the patient chooses to complete the survey on her own. The patient should be instructed to respond to questions in terms of her experience during the time frame specified on the form. It is permissible to assist the patient with completion of the forms, as long as the staff person does not influence the patient's response.
- 5.6.3 The completed forms must be reviewed by the designated CRN or CRA, as soon as the patient completes them, to ensure all items were marked appropriately. If more than one answer was marked, the patient should be asked to choose the answer which best reflects how she is feeling. If a question was not answered, the patient should be asked if she would like to answer it. The patient should always have the option to refuse. If the patient refuses, it should be indicated on the form that she declined to answer the item.
- 5.6.4 If the patient cannot complete the baseline form properly, the reason should be noted on the Assessment Compliance Form. If a patient cannot complete the follow-up questionnaire because she is too sick AND the CRN/CRA learns of it, it will be documented on the Assessment Compliance Form.

Rev. 11/16

- 5.6.5 The clinician responsible for filling out the **Provider Reproductive Health Values Surveys (Specific to Patient)** may be the treating MD, the nurse practitioner, or PA-C involved in the clinical care of the patient. This will be determined per patient by the CRA/CRN.
- 5.6.6 If overlap occurs between the patient study follow-up visit and chemotherapy/radiation treatment visit, the Patient Follow-up Interviews should be completed rather than the Patient Follow-up Interview During Chemotherapy.

Rev. Add11

5.7 On-Study and Follow Up Assessment Schedule

5.7.1 Provider Assessment Schedule

Providers (oncology staff, i.e. MD, nurse practitioner or PA-C, that clinically assesses the patient) from both arms will complete two surveys, the **Provider Reproductive Health Values Survey (General)** and the **Provider Reproductive Health Values Survey (Specific to Patient)**. The general survey consists of 18 questions which assess provider opinion regarding reproductive health and cancer care and referral practices. The patient specific survey

Rev. 11/16
Rev. 5/17

consists of 8 questions assessing provider opinion regarding the reproductive health care needs of a specific patient.

Providers will complete the **Provider Reproductive Health Values Survey (General)** at the following two timepoints. This survey will take approximately 5 minutes to complete.

1. Pre-Study (0 months)
2. 30 months from site initiation

Additionally, the provider will complete the **Provider Reproductive Health Values Survey (Specific to Patient)** at the following eight timepoints:

1. Baseline - (0 months)
2. 3 Months from Baseline Visit
3. 6 Months from Baseline Visit
4. 12 Months from Baseline Visit
5. 24 Months from Baseline Visit

Study Staff will complete forms according to the following schedule:

Medical Record Abstraction Form - Baseline

1. Baseline

Medical Record Abstraction Form – Follow-up

NOTE: The term 'regimen' is defined as anytime a patient starts a new course of medical treatment.

1. Within one week prior to the start of each chemotherapy regimen for patients undergoing chemotherapy or every four weeks of RT for patients undergoing radiation therapy alone
2. 3 Months from Baseline Visit
3. 6 Months from Baseline Visit
4. 12 Months from Baseline Visit
5. 24 Months from Baseline Visit

5.7.2 Patient Reported Outcomes Assessment Schedule

If a patient is eligible to participate in this study and the physician approves, the study is further discussed with the patient. Patients providing consent will be registered on trial. Participants will complete a total of 8 assessment visits (including baseline). Structured interviews will be administered to participants at the timepoints listed below. At each time point, two questionnaires will be administered by a study team member. Completion of these forms on a given visit should take about 10-20 minutes. Patient interviews are designed to assess the patient's reproductive health history, management and goals at baseline and as they progress through cancer treatment. Additionally, the Sexual Function Survey, which includes the PROMIS Sexual Function Brief Profile v1.0 – Female, is designed to assess sexual health at diagnosis and throughout treatment.

Patients will be assessed according to the following schedule:

Rev. Add8

Patient Baseline Interview (51 Questions)

Baseline

Patient Follow-Up Interview (34 Questions)

1. 3 Months from Baseline Visit
2. 6 Months from Baseline Visit
3. 12 Months from Baseline Visit
4. 24 Months from Baseline Visit

Patient Interview - During Chemotherapy/Radiation Treatment (11 Questions)

In addition to the above forms, each patient will complete the **Patient Interview During Chemo/Radiation Treatment** as well according to the following schedule:

Within one week prior to the start of each chemotherapy regimen for patients undergoing chemotherapy or every four weeks of RT for patients undergoing radiation therapy alone

Sexual Function Survey (16 Questions)

1. Baseline
2. Within one week prior to the start of each chemotherapy regimen for patients undergoing chemotherapy or every four weeks of RT for patients undergoing radiation therapy alone
3. 3 Months from Baseline Visit
4. 6 Months from Baseline Visit
5. 12 Months from Baseline Visit
6. 24 Months from Baseline Visit

5.8 Provision of Appropriate Care for Patients

The clinical management of all patients (regardless of symptom severity) will be determined by the treating physician.

5.9 Reproductive Health Related Endocrine Disruption in Cancer Care

This part of the study will be conducted on the first 200 patients enrolled in the EROS study who agree to participate. Blood samples will be drawn and laboratory tests (AMH, FSH, Thyroperoxidase antibody and TSH) will be evaluated to assess fertility status and endocrine disruption at baseline and at 3, 6, 12, and 24 months from Baseline Visit.

5.10 Quality of Life (QOL) Assessment

The Sexual Function Survey will be administered to all patients recruited for the EROS study over the 2 year study period (as specified in Table 1). The PROMIS Sexual Function Brief Profile v1.0 - Female measures are included in the Sexual Function Survey.

5.11 Duration of Study

Patients will participate on this study for 24 months from registration.

Rev. Add11

Rev. Add11

Rev. Add11

Patient will complete surveys in this study unless:

- Extraordinary Medical Circumstances: If at any time the constraints of this protocol are detrimental to the patient's health, administration of protocol surveys should be discontinued. In this event submit data through Medidata Rave according to the schedule in the E1Q11 Forms Completion Guidelines.
- Patient withdraws consent.

5.12 Duration of Follow-up

For this protocol, all patients, including those who discontinue study participation early, will be followed for survival for 2 years from the date of registration.

Rev. Add11

6. Measures

6.1 Study Tools

Forms completed by clinical staff:

- 6.1.1 The EROS Trial: Engendering Reproductive Health Within Oncologic Survivorship Provider Reproductive Health Values Survey (General*).
- 6.1.2 The EROS Trial: Engendering Reproductive Health Within Oncologic Survivorship Provider Reproductive Health Values Survey (Specific to Patient*).
- 6.1.3 The EROS Trial: Engendering Reproductive Health Within Oncologic Survivorship Medical Record Abstraction Form – Baseline.
- 6.1.4 The EROS Trial: Engendering Reproductive Health Within Oncologic Survivorship Medical Record Abstraction Form – Follow-up.
- 6.1.5 The EROS Trial: Engendering Reproductive Health Within Oncologic Survivorship Pregnancy Supplement Form.
- 6.1.6 The EROS Trial: Engendering Reproductive Health Within Oncologic Survivorship Reproductive Health Assessment. (for intervention sites only)

Semi-Structured Interviews to be administered to study participants:

[figure not shown]
- 6.1.7 The EROS Trial: Engendering Reproductive Health Within Oncologic Survivorship Patient Baseline Interview.
- 6.1.8 The EROS Trial: Engendering Reproductive Health Within Oncologic Survivorship Sexual Function Survey.
- 6.1.9 The EROS Trial: Engendering Reproductive Health Within Oncologic Survivorship Patient Interview – During Chemotherapy/Radiation Treatment.
- 6.1.10 The EROS Trial: Engendering Reproductive Health Within Oncologic Survivorship Patient Follow-up Interview.

***Providers (oncology staff, i.e. MD, nurse practitioner or PA-C, that clinically assesses the patient) are required to review, sign, and submit a Provider Consent Form prior to site initiation of this study.**

7. Study Parameters (For Arm A only)

[figure not shown]
NOTE: THE ASSESSMENT SCHEDULE FOR THE INTERVENTION ARM B (WITH SOME EXTRA ITEMS) IS AVAILABLE IN ADDENDUM I.

Site Specific Timeline

Subject Specific Timeline

Rev. Add10
Rev. Add11

Rev. 5/17
Rev. Add11

Table 1. Non-Intervention (Arm A) Engendering Reproductive Health within Oncologic Survivorship: Data Collection

For Intervention Arm (Arm B) data collection table includes four additional items located in Addendum I

NOTE: The term 'regimen' is defined as anytime a patient starts a new course of medical treatment.

Rev. Add10

	Pre-study ¹	Baseline ⁴	0 and 30 Months from Site Initiation	Within one week prior to start of each Chemotherapy Regimen or Every Four Weeks during RT ^{10,11}	At the end of 3, 6, 12, 24 Months from Baseline Visit ^{11,12}
SITE²					
Provider Consent Form	X				
Delegation of Responsibilities Log	X				
CLINICIAN					
Provider Reproductive Health Values Survey (General) ³	X		X		
Provider Reproductive Health Values Survey (Specific to Patient) ⁵		X			X
Medical Record Abstraction Form – Baseline ⁶		X			
Medical Record Abstraction Form – Follow-up ^{6,13}				X	X
Pregnancy Test ⁷		X		X	X
Pregnancy Supplemental Form ⁸		X		X	X
PATIENT					
Patient Baseline Interview ⁹		X			
Sexual Function Survey		X		X	X
Patient Interview - During Chemotherapy/Radiation Treatment ¹⁰				X	
Patient Follow-up Interview ^{11, 12}					X

1. Pre-Study documents should be completed prior to participant recruitment.
2. These documents need to be updated based on staffing and provider changes over the course of this study. We define provider as the clinician (MD, nurse practitioner or PA-C) that clinically assesses the oncology patient.
3. Each primary clinician should complete this form once at 0 (Prior to Study Training) and 30 months from site initiation. It is not necessary to fill out the form for each patient at each of these time points. As staffing changes over the course of this study new clinicians will complete this form

Rev. 11/16

Rev. Add8 upon signing provider consent and at 30 months from site initiation. The date for site initiation is defined as the time when the site is approved to enroll patients into this study.

Rev. Add10 4. Patient will have the baseline provider visit, complete baseline surveys and be registered to the trial on the same day of consent. If this is not feasible, then all baseline requirements (including registration) must be completed within one week of patient consent and before treatment initiation as part of their standard of care (i.e., chemotherapy or radiation therapy). Baseline provider visits, completion of baseline surveys and study registration must be completed on same day.

5. This form should be completed by the primary clinician after each office visit (as determined by the CRN/CRA)

6. Complete the medical record abstraction forms from the medical chart of each eligible participant after visit with the patient. Form must be completed and entered electronically in Medidata Rave within one week of patient visit.

7. Pregnancy Test requirements. All patients must be counseled about pregnancy precautions, risks of fetal exposure and other risk as per standard of care. Pregnancy tests should be administered at Baseline, 3, 6, 12, and 24 months from Baseline Visit and within one (1) week prior to each chemotherapy regimen. For patients on radiation therapy (RT) alone, pregnancy tests should be administered within one (1) week prior to the initiation of radiation therapy then every four (4) weeks until the end of radiation treatment. For patients who aged past 55 after enrollment may discontinue pregnancy tests if menopause is confirmed FSH < 23mIU/mL. Patients who have had a hysterectomy after enrollment may also discontinue pregnancy tests. Pregnant patients may discontinue pregnancy tests until delivery

Rev. Add10 8. If patient is pregnant or has been pregnant since her last study visit, one Pregnancy Supplement Form should be completed for each pregnancy.

9. Interview done after visit with the provider.

10. Study surveys should be completed at the beginning of each regimen of cancer treatment. For patients undergoing chemotherapy, surveys should be administered within one (1) week prior to each chemotherapy regimen. For patients on radiation therapy (RT) alone, surveys should be administered within one (1) week prior to the initiation of radiation therapy then every four (4) weeks until the end of radiation treatment. Patients receiving both chemotherapy and RT must follow the chemotherapy reporting schedule; if patient's treatment overlaps (+/- 2 weeks), the questionnaires do not have to be repeated.

Rev. Add10 11. Sites must complete the study surveys within the following windows:

- 3-month visit: +/- one month
- 6-month visit: +/- one month
- starting from 12-month visits: +/- 2 months

12. If there is an overlap (+/- 2 weeks) of visits at 3, 6, 12, and 24 months and visits relating to chemotherapy or RT, the Medical Record Abstraction-Follow up, Patient Follow-up Interview, the Sexual Function Survey and the Pregnancy Test only need to be completed once at the 3, 6, 12, and 24 month visits and not at the chemotherapy or RT visits.

13. The term 'regimen' is defined as anytime a patient starts a new course of medical treatment

Table 2. Biological Sample Submissions

NOTE: Effective March 10, 2021 the endocrine marker sub-study is closed to further accrual. This sub study has met its targeted accrual goal.

Serum specimens should continue to be collected from previously enrolled patients that have consented to provide serum specimens at the time points outlined below.

Do not submit serum specimens from patients registered to E1Q11 after March 10, 2021.

NOTE: THIS SECTION APPLIES TO BOTH STUDY ARMS.

Blood samples should be submitted for the endocrine markers as outlined in Section 9. Submit only from patients who have given written consent to participate in the optional laboratory studies.

NOTE: It is required that biological sample submissions be logged into the ECOG-ACRIN Sample Tracking System (STS) for purposes of monitoring compliance.

NOTE: Institutions must complete and submit the Quest Diagnostics Sub-Account Information Sheet ([Appendix III](#)) to create their study specific account number in order to obtain supplies and arrange for courier service for the collection of the blood samples. See Section 9 for further instructions.

Biological Materials	Day of Registration [prior to treatment] ¹	Within One Week Prior to Start of Each Chemotherapy Regimen or Every Four Weeks during RT ¹	At the end of 3, 6, 12, 24 Months from Baseline Visit
From Patients Who Answer "Yes" to "I agree to participate in the laboratory research studies that are being done as part of this clinical trial."³			
Serum (one 7.5mL red top tube) ^{2,3,4}	X	X	X
Serum, SST (one 7.5mL red/black top tube) ^{2,3,4}	X	X	X

1. For patients undergoing chemotherapy, blood samples will also be collected in conjunction with chemotherapy within one (1) week prior to the start of each chemotherapy regimen. For patients undergoing radiation therapy (RT) alone, blood samples will be collected within one (1) week prior to the initiation of radiation therapy and every four (4) weeks until the end of radiation treatment.
2. When possible, blood draws will be timed with the collection of blood draws for routine clinical purposes thus minimizing participant burden.
3. Ship blood samples to Quest Diagnostics as outlined in Section 9.
4. Supplies are available for the collection of the blood samples.

Rev. 11/17	8. Statistical Considerations
Rev. Add8	The primary objective of this study is to evaluate the success of implementation of the reproductive health programming among females aged between 15-55 years old with initial diagnosis of any form of cancer (before chemotherapy or radiation has started). Secondary objectives include (1) assessing the degree of discrepancy between patients and their clinicians in estimates of significance of the reproductive health goals for the patient, (2) evaluating baseline and follow-up reproductive health assessments for trends in reproductive health choices relating oncofertility, oncocontraception, and pregnancy over the 2 year study period, (3) identifying clinical and demographic factors that predict the adequacy of reproductive health management.
Rev. Add9	
Rev. Add11	
Rev. 11/17	E1Q11 is a cluster randomized trial (CRT) with patients in one site all receiving the same intervention. This study was originally designed with a paired-matching cluster randomization, paired mainly by the type of institution (MU NCORP vs. NCORP) and geographical region (Northeast vs. Midwest vs. South vs. West). However, this design falls apart as some sites originally invited to participate in this study dropped from the study (at various time points). Consequently, the study design is now changed to a parallel cluster randomization (i.e., with clusters randomized to one of treatment arms). To have a manageable number of patients in this study and have this study completed in a reasonable timeline, the sample size was re-calculated based mainly on the primary endpoint of the primary objective (instead of the important secondary endpoint of the primary objective) and the patient's age limit was lowered to 15 years. Due to an oversight in previous sample size calculations, the sample size was re-calculated in amendment 13.
Rev. Add8	
Rev. Add9	8.1 Design and Randomization
Rev. Add10	
In this study, the patient population will include all female patients initially diagnosed with any form of cancer and within the reproductive age of 15-55 years old. All enrolled female patients will be categorized into one of the four strata (Figure 1) – Stratum 1 with patients who are not pregnant, sexually active, and have not completed childbearing, Stratum 2 with patients who are not pregnant, sexually active, and have completed childbearing, Stratum 3 with patients who are not pregnant and not sexually active, and Stratum 4 with pregnant females and females who are interested in becoming pregnant within one year of study enrollment.
 
Given that E1Q11 adopts a cluster randomized design, the details of endpoints can be found in the statistical analysis plan (located in Addendum II) in order to avoid contaminating control sites and to preserve the integrity of the intervention.
 
To evaluate the success of the intervention, appropriate reproductive health management will be used as the primary endpoint and the sample size will be calculated based on this endpoint. It is expected that the intervention can increase appropriate reproductive health management from 50% to 80% (across all four strata). The baseline rate of 50% was determined by Pilot Study 1 data.^{21,22} In the “Reproductive Health Algorithm,” 100% of females had appropriate reproductive health management after the intervention.²³ Therefore, with this study, we expect to detect an improvement from 50% to 80%.
 
For the secondary endpoint of LTC, it is hypothesized that for patients in Stratum 1, intervention will increase the contraception usage rate from 1% to 22% (based on Pilot Study 1). For patients in Stratum 2, the intervention will increase the

[figure not shown]
contraception usage rate from 20% to 60% (based on Pilot Study 1 and the “Reproductive Health Algorithm”)^{23,21,22}. Stratum 3 and Stratum 4 are observational groups and no specific hypothesis is given for them.

Institutions will be selected and invited to participate in this study. Because of the logistical difficulties of having both intervention and no intervention programs within a single institution, the unit of randomization will be the institution (i.e., a cluster randomized approach) rather than the individual patient. Thus, institutions participating in the study will be randomized to one of the two arms, Arm A without intervention and Arm B with intervention. Patients being accrued to the study, regardless of stratum, will be assigned to one of the two arms depending on the institutional assignment.

Figure 1. Patient Strata

Rev. 11/17

Rev. Add10

1. Defined as within one year from study enrollment) for the phrase “Immediate Pregnancy.

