3.1 Eligibility Criteria

Rev. 11/17	_____ 3.1.1	Female patients presenting with initial diagnosis of any type of cancer, including patients with DCIS.
Rev. Add8	_____ 3.1.2	Patients must not have initiated chemotherapy, radiation therapy or endocrine therapy prior to registration to this study.
Rev. 11/17	_____ 3.1.3	Patients must not have had a prior hysterectomy, bilateral oophorectomy or sterilization of any method.
Rev. Add9	_____ 3.1.4	Patients must be pre-menopausal patients within the reproductive age range of 15-55 years. Please note, pre-menopausal will be defined as females meeting the following criteria: 
• Patients not currently on hormonal contraception with the presence of menses in the past 6 months.• If no menstruation in the past 6 months, without hormonal manipulation, then confirmed FSH < 23mIU/mL• If age < 47 years and on hormonal contraception, then patient will be eligible regardless of menstrual history• If age ≥ 47 years and on hormonal contraception, then FSH confirmed < 23mIU/mL
Rev. Add10	_____ 3.1.5	Pregnant females are eligible to participate in this study.
Rev. Add10	_____ 3.1.6	Patients must have the cognitive ability to participate in the study.

Rev. 11/17 4. CTEP Registration Procedures

Rev. Add8
Rev. Add11

Food and Drug Administration (FDA) regulations and National Cancer Institute (NCI) policy require all individuals contributing to NCI-sponsored trials to register and to renew their registration annually. To register, all individuals must obtain a Cancer Therapy Evaluation Program (CTEP) Identity and Access Management (IAM) account (<https://ctepcore.nci.nih.gov/iam>). In addition, persons with a registration type of Investigator (IVR), Non-Physician Investigator (NPIVR), or Associate Plus (AP) must complete their annual registration using CTEP's web-based Registration and Credential Repository (RCR) (<https://ctepcore.nci.nih.gov/rcr>).

RCR utilizes five person registration types.

- IVR — MD, DO, or international equivalent;
- NPIVR — advanced practice providers (e.g., NP or PA) or graduate level researchers (e.g., PhD);
- AP — clinical site staff (e.g., RN or CRA) with data entry access to CTSU applications (e.g., Roster Update Management System (RUMS), OPEN, Rave,);
- Associate (A) — other clinical site staff involved in the conduct of NCI-sponsored trials; and

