8.4 Accrual Goal and Accrual Period

To help safeguard 10 enrolling sites per intervention group (as originally proposed), we have invited more than 20 MU NCORPs/NCORPs to participate in this study (as listed on the cover page of the protocol). To further help accrual, we lowered the age limit to 15 years in Addendum 9 (effective from February 6, 2019). Besides the original participating MU NCORPs/NCORPs, interested pediatric MU NCORPs/NCORPs are allowed to participate in the EROS trial as well.

To have adequate power to detect the difference from 50% to 80% in the primary endpoint, the accrual goal of this study was re-calculated to ensure 149 patients in the intervention arm, assuming 16 sites enrolling patients for this trial (8 to the non-intervention group (Arm A) and the other 8 to the intervention group (Arm B)). Patients from each site will be enrolled into one of the four strata depending on the patient's pregnancy status, sexual activity status, and/or her birth intention. Given some sites accrue much faster than the others, a NCORP accrual cap of 45 patients was implemented per Addendum 8.

As of January 4, 2021, 268 patients from 9 Arm A sites and 138 patients from 8 Arm B sites have had been enrolled to this trial. As this is a comparative study, the trial will continue accrual for both arms until Arm B meets its accrual goal of 149 patients which is projected to take another 5 months. Taking into account the site accrual up to January 4, 2021 and the accrual rate in the past three months (i.e., the last three months of 2020, with the top three accrual sites met the accrual cap of 45 patients and closed accrual to Arm A), the final accrual of this study, thus, is expected to be 425 patients (276 from Arm A and 149 from Arm

Rev. Add11

Rev. Add8
Rev. Add9

B). The mean cluster size is projected to be 25 patients assuming 17 enrolling sites in total (~30 patients per cluster for Arm A and ~18 patients per cluster for Arm B). As suggested by Table 1, this study is equipped with more power if the cluster size is larger than the average of 18-19 patients per cluster and/or if the number of clusters per arm is greater than the stated 8 sites per arm in the sample size calculations. The additional patients and sites in Arm A imply the power of this study will be a little larger than stated (i.e., 85% power) to detect a change from 50% to 80% on the primary endpoint with the projected final accrual of 425 patients.

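### The FSH inequality in Table 1 footnote 7 is reversed: the value that confirms menopause there confirms pre-menopausal status in Section 3.1.4

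*Combined protocol and SAP*

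**What the plan says.** Section 3.1.4 limits entry to women who have not reached menopause: "Patients must be pre-menopausal patients within the reproductive age range of 15-55 years". Two of its four bullets rest on FSH:

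- no recent menses: "If no menstruation in the past 6 months, without hormonal manipulation, then confirmed FSH < 23mIU/mL"
- older women on hormonal contraception: "If age ≥ 47 years and on hormonal contraception, then FSH confirmed < 23mIU/mL"

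In both, a value below 23 mIU/mL makes the patient eligible as pre-menopausal.

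Table 1 in Section 7 schedules pregnancy tests for Arm A. Its footnote 7 gives the fixed visits, "Pregnancy tests should be administered at Baseline, 3, 6, 12, and 24 months from Baseline Visit", and adds a test in the week before each chemotherapy regimen. For radiotherapy alone, there is a test in the week before the start and then one every four weeks until it ends. The same footnote sets the exemption for older patients: "For patients who aged past 55 after enrollment may discontinue pregnancy tests if menopause is confirmed FSH < 23mIU/mL".

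Table 7 in Section 8.6.3 lists FSH of 23.0 mIU/mL or more as the abnormal range for ages 15 to 55.

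**The concern.** One marker, with one cut-off and one direction, supports opposite conclusions: pre-menopausal at entry, menopausal in follow-up. Footnote 7 is an operative instruction, and it holds the only FSH rule sites are given for stopping pregnancy tests.

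Followed as written, it errs in both directions. A patient past 55 with FSH below 23 may stop testing, although the protocol would have called that value pre-menopausal at entry. A patient with FSH of 23 or more does not meet the exemption, although she is evidently the one it was written for. A site that sensibly stops testing her departs from the written rule.

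The first error matters more, because the tests before chemotherapy regimens and during radiotherapy relate to fetal exposure, a risk the footnote itself names.

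**Working it through.** **Direction of the rule.** There is no figure of the plan to reproduce here, so the check is a comparison of the texts.

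| Place | FSH < 23 mIU/mL | FSH ≥ 23 mIU/mL |
|---|---|---|
| Section 3.1.4 (no menses in 6 months; age 47 or over on hormonal contraception) | pre-menopausal, eligible | not confirmed pre-menopausal |
| Section 8.6.3, Table 7 | not in the abnormal range | abnormal |
| Section 7, Table 1 footnote 7 | menopause confirmed, tests may stop | menopause not confirmed, tests continue |

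The third row contradicts the first. Section 3.1.4 settles the matter alone. Table 7 agrees, but it is only supporting evidence, because its abnormal ranges for other markers look questionable. A fault in reading the PDF is unlikely: the ≥ sign comes through correctly in Sections 3.1.4 and 8.6.3. The footnote is current text, not an amendment log.

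**Who can be affected.** Section 5.11 fixes follow-up: "Patients will participate on this study for 24 months from registration". Take passing 55 to mean turning 56, and eligibility to run to the 56th birthday. Then

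months to 56th birthday = (56 − age at registration) × 12,

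and the rule covers the scheduled tests at 3, 6, 12 and 24 months that fall on or after that month.

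| Age at registration | Months to 56th birthday | Scheduled tests covered |
|---|---|---|
| below 54.0 | more than 24 | 0 |
| 54.0 | 24 | 1 (month 24) |
| 55.0 | 12 | 2 (12, 24) |
| 55.5 | 6 | 3 (6, 12, 24) |
| 55.75 or over | 3 or fewer | 4 (3, 6, 12, 24) |

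Any treatment-linked test after the birthday comes on top. If passing 55 instead means passing the 55th birthday, the lower bound becomes 53, since (55 − 53) × 12 = 24.

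**How many patients.** Section 8.4 gives the projected final accrual, which "is expected to be 425 patients (276 from Arm A and 149 from Arm" B. The documents give no age distribution. The share in the age band is therefore an assumption, taken as 1% to 5%:

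- Arm A: 276 × 0.01 = 2.8 and 276 × 0.05 = 13.8, so about 3 to 14.
- Both arms: 425 × 0.01 = 4.25 and 425 × 0.05 = 21.25, so about 4 to 21.

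The second line applies only if Arm B has the same footnote. Table 1 covers Arm A, and Section 7 says of the other arm: "THE ASSESSMENT SCHEDULE FOR THE INTERVENTION ARM B (WITH SOME EXTRA ITEMS) IS AVAILABLE IN ADDENDUM I". That addendum is not among the documents reviewed.

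**The case against.** The best counter-argument accepts the slip and disputes the remedy. Section 3.1.4 is an entry test before treatment; it never says that FSH of 23 or more confirms menopause. Table 7 uses that threshold for endocrine disruption, not menopause. Footnote 7 applies after enrolment, when many patients will have been treated, and Section 1.7 itself warns that FSH depends on the ovulatory cycle and is affected by tamoxifen and other hormonal therapy. Reversing the sign could allow testing to stop on a treatment-related rise. The error might also be an eligibility phrase copied across, with some other criterion intended.

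This is a fair limit on FSH as a marker, but it applies to the sponsor's choice of an FSH rule whichever way the sign points. The proposed correction keeps the sponsor's marker and cut-off and makes the footnote the complement of Section 3.1.4. If the sponsor intended a different criterion, it can say so in the same amendment.

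The other objections reduce the size of the point and do not remove it:

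- The exemption is permissive, pregnancy counselling is required for everyone, and Section 5.8 leaves clinical management to the treating physician. All true, and the reason the risk is low; none of it makes the printed value correct.
- The counts take in everyone in the age band. Harm also needs an FSH below 23, a site that applies the text literally and a patient who can still conceive. The counts are therefore upper figures for reach, not for harm.
- By January 4, 2021, 268 of the projected 276 Arm A patients were enrolled, so an amendment reaches only the follow-up that remains.
- Table 1 footnote 11 allows 2 months either side for surveys from month 12. If pregnancy tests follow those windows, the lower age bound moves to 56 − 26/12, about 53.8. This is immaterial.

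**Conclusion.** The concern holds, with high confidence. It is a drafting error in a safety-related decision threshold and should be corrected.

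The consequence is small. It is confined to patients near the upper age limit, on the assumed 1% to 5% share and on the reading that passing 55 means turning 56. For them it governs one to four of the four scheduled follow-up tests, plus any treatment-linked tests after the birthday. The Arm B part depends on an addendum that was not available. The 3-month primary endpoint, the sample size and the power do not depend on this rule, and the 2-year pregnancy analysis in Section 8.6.1 is not plausibly affected.

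**What to change.** Amend the exemption in Table 1 footnote 7 to read along these lines: *a patient who passes age 55 after enrolment may stop pregnancy tests once menopause is confirmed by FSH ≥ 23 mIU/mL.* Send sites a short notice of the correction. Check the Arm B schedule in Addendum I and correct it too if it carries the same footnote.

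The cost is a one-line protocol amendment and the notice. Data collection, sample size and analysis stay as they are.
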